7.3. Study Endpoints

7.3.1. Primary Endpoints

The co-primary endpoints are:

- Safety as assessed by adverse events (AEs), vital signs, ECGs, and clinical laboratory tests (includes patients with HSCT-TMA, aHUS, and TTP)
- For HSCT-TMA patients, response to OMS721 treatment. A responder is defined as a patient with HSCT-TMA who demonstrates improvement in laboratory TMA markers (platelet count and LDH) and clinical benefit (either improvement in organ function or reduction in transfusion burden). The specific criteria are defined as follows:
 - Improvement in laboratory TMA markers:
 - Platelet count:
 - For patients with baseline platelet count $\leq 20,000/\mu\text{L}$:
 - Tripling of baseline platelet count
and
 - Post baseline platelet count $> 30,000/\mu\text{L}$
and
 - No platelet transfusions 2 days before and on the day of the platelet count collection
 - For patients with baseline platelet count $> 20,000/\mu\text{L}$
 - Increase in platelet count $\geq 50\%$
and
 - Post baseline platelet count $> 75,000/\mu\text{L}$
and
 - No platelet transfusions 2 days before and on the day of the platelet count collection
 - and**
 - LDH:
 - $\text{LDH} < 1.5 \times \text{upper limit of normal (ULN)}$
 - and**
 - Improvement in clinical status:
 - Improvement in organ function as evidenced by any of the following:
 - Improvement in renal function:

CONFIDENTIAL

No use, disclosure or reproduction outside of Omeros without prior written authorization

- Reduction of creatinine > 40%
- or
- Creatinine < ULN and reduction of creatinine > 20%
- or
- Discontinuation of renal replacement therapy (RRT)

or

- Improvement in pulmonary function:
 - Extubation and discontinuation of ventilator support
- or
- Discontinuation of non-invasive mechanical ventilation (continuous positive pressure ventilation)

or

- Improvement in neurological function:
 - Improvement in reversible neurological conditions (e.g., cessation of seizures)
- or
- Stabilization of irreversible neurological conditions (e.g., stability of neurological deficits following stroke without further deterioration or subsequent strokes)

or

- Improvement in gastrointestinal function (gastrointestinal HSCT-TMA will require diagnosis by tissue biopsy):
 - Improvement measured by improvement in the gastrointestinal measures in the Mount Sinai Acute GVHD International Consortium (MAGIC) criteria

or

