13.2.1. General Considerations

All data summaries will be descriptive in nature. Summary statistics for continuous variables will include number of patients, mean, median, standard deviation, minimum, and maximum. For categorical variables, frequencies and percentages will be provided. When required for the statistical analysis of a particular variable, the baseline value will be the last recorded value prior to the administration of the first dose of study treatment. There are 2 exceptions. The baseline platelet count is defined as the average of the 2 predose values. The baseline creatinine is defined as the maximum creatinine value between the diagnosis of TMA and 4 weeks after the first dose of OMS721.

Statistical analyses will be focused on the HSCT-TMA patients and will be summarized by OMS721 dose (4.0 mg/kg, 370 mg, and both doses combined). Atypical hemolytic uremic syndrome and TTP patients will be summarized separately by OMS721 dose.

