Haptoglobin	See laboratory measure schedule ¹	Collect from the clinical chart. Overlapping data will also be available from the central laboratory on some dates.
Creatinine	See laboratory measure schedule ¹	Collect from the clinical chart. Overlapping data will also be available from the central laboratory on some dates.
Bilirubin	See laboratory measure schedule ¹	Collect from the clinical chart. Overlapping data will also be available from the central laboratory on some dates.
Aspartate aminotransferase	See laboratory measure schedule ¹	Collect from the clinical chart. Overlapping data will also be available from the central laboratory on some dates.
Alanine aminotransferase	See laboratory measure schedule ¹	Collect from the clinical chart. Overlapping data will also be available from the central laboratory on some dates.
Alkaline phosphatase	See laboratory measure schedule ¹	Collect from the clinical chart. Overlapping data will also be available from the central laboratory on some dates.
Coombs	Each instance	Collect from the clinical chart. Overlapping data will also be available from the central laboratory on some dates.

CONFIDENTIAL

No use, disclosure or reproduction outside of Omeros without prior written authorization

Variables	Timing/Periodicity of Data Collection	Data Collection Rules/Definitions
Schistocytes	See laboratory measure schedule ¹	Collect from the clinical chart. Overlapping data will also be available from the central laboratory on some dates.
Others abnormal	See laboratory measure schedule ¹	Collect from the clinical chart. Overlapping data will also be available from the central laboratory on some dates.

Abbreviations: CMV = cytomegalovirus; DAH = diffuse alveolar hemorrhage; GVHD = graft-versus-host disease; HLA = human leukocyte antigen; HSCT = hematopoietic stem cell transplant; IPS = idiopathic pneumonia syndrome; LDH = lactate dehydrogenase; RBC = red blood cell; TMA = thrombotic microangiopathy; VOD = veno-occlusive disease.

¹ Laboratory measure schedule: Laboratory measures will be collected according to the schedule as outlined below.

CONFIDENTIAL

No use, disclosure or reproduction outside of Omeros without prior written authorization

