19.5. Laboratory Measure Schedule

As available, local laboratory measures of platelet count, Hgb, white blood cell count, absolute neutrophil count, LDH, haptoglobin, creatinine, bilirubin, AST, ALT, alkaline phosphatase, and schistocytes will be collected according to the following schedule:

Pre-TMA period:

- Once immediately prior to conditioning
- On Day -1 or 0 prior to transplant (the measure closest to the transplant). (Day 0 is the day of transplant)
- On Days +2, +4, +6, +8, +10, +14, +21, +28 following transplant and weekly thereafter until 28 days prior to the diagnosis of TMA

TMA period:

- Daily from 28 days prior to the diagnosis of TMA to the later of 12 weeks following the diagnosis of TMA or 4 weeks following resolution of TMA

Post-TMA period:

- Once weekly following the TMA period for 4 weeks, then once every 2 weeks for 4 weeks, and then once monthly \pm 3 days until up to 2 years following the first dose of OMS721

Platelet count should be recorded immediately before and after each platelet transfusion.

Hemoglobin levels should be recorded immediately before and after each RBC transfusion.

Abbreviations: ALT = alanine aminotransferase; AST = aspartate aminotransferase; Hgb = hemoglobin; LDH = lactate dehydrogenase; RBC = red blood cell; TMA = TMA = thrombotic microangiopathy.

CONFIDENTIAL

No use, disclosure or reproduction outside of Omeros without prior written authorization

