2.5. Study Endpoint Baseline

In general, the baseline of a study endpoint is the last observation prior to the first study drug administration except for platelet count.

The baseline of a laboratory parameter will be based on the central laboratory values except for platelet count.

Platelet counts from the central laboratory are to be used in the calculation of baseline. If a central laboratory value is not available and its local laboratory value is available on the same collection date, the local laboratory value will be used. In addition, if there are at least 2 platelet count collections on the same date, the first one will be used.

Baseline platelet count is defined as the average of values obtained on different days in the week (including Day 1) prior to the first dose of OMS721. If more than 3 such values are available, then the 3 values that are most proximate to the first dose of OMS721 should be used. [Table 2](#) is an example of a baseline platelet count calculation.

Table 2: Example of Baseline Platelet Count Calculation

Study Day	Central Lab	Local Lab	Value to be used to Determine Baseline
-5	Yes	Yes	Not used
-4	Yes	Yes	Central lab
-3	No	Yes	Local lab
-2 (1 st)	No	Yes	Not used
-2 (2 nd)	Yes	No	Central lab
-2 (3 rd)	Yes	Yes	Not used

In addition, if at least 1 central laboratory value is used in the baseline calculation, the reference range of the central laboratory will be used to determine the toxicity grade according to National Cancer Institute (NCI) Common Terminology Criteria for Adverse Events (CTCAE). If the baseline value is calculated from local laboratory values only, then the reference range of the local laboratory will be used.

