2.8.2. Efficacy Analyses

2.8.2.1. Primary Efficacy Endpoint

A patient is a responder if this patient meets the responder criteria (Section 2.1) at any time post-baseline during the study. If a patient is not evaluable for a response criterion due to confounding factors, the non-evaluable response criterion will not be included in the determination of responder. Evaluability of each response criterion will be determined by a clinical review of relevant data and will be documented in the clinical study report. For example, potential confounding factors include graft failure for platelet count or transfusions, and nephrotoxic medications for renal function. Furthermore, laboratory values collected from both the local laboratories and the central laboratories will be used to determine response status.

Analysis of the primary efficacy endpoint will use a non-responder imputation to impute missing or incomplete data to evaluate response. The number and percent of responders will be summarized with exact 95% CI (Clopper-Pearson) by dose and total for the FAS and PAS

populations. If the lower bound of the exact 95% CI is greater than 15%, there is sufficient evidence to demonstrate efficacy of narsoplimab in the target patient population. Each criteria of the response will be listed for each patient.

Sensitivity analyses will include:

1. Subgroup analyses for the following subgroups will be performed for the FAS population:
 - Age (< 65 , ≥ 65 years)
 - Gender (Male or Female)
 - Graft-versus-host disease (GVHD) (Yes or No)
 - Significant infection (Yes or No)
 - Graft failure or non-engraftment (Yes or No)
 - Female-to-male transplant (Yes or No)
 - Multiple organ TMA involvement (Yes or No)
 - Mismatched donor (Yes or No)
 - Baseline platelet counts ($< 20,000$ or $\geq 20,000$ platelets/ μL)
 - Renal dysfunction at baseline (Creatinine $> \text{ULN}$ or spot urine protein $\geq 2+$ or > 30 mg/dL; Yes or No)
 - Any transfusions within the 2 weeks prior to or on the first OMS721 dose date (Yes or No)
2. A completer analysis will be performed using the patients with non-missing responses only. Exact 95% CI for the completer response rate will be provided for the FAS population by dose.
3. Two alternative definitions of response will be analyzed:

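### Creatinine results are not paired by laboratory in the renal response: a central baseline can be set against a local follow-up value, so a between-laboratory difference can supply, or hide, part of the required fall

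*Protocol*

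**What the plan says.** **Criterion.** Protocol 7.3.1 and SAP 2.1 count renal improvement as "Reduction of creatinine > 40"%, or "Creatinine < ULN and reduction of creatinine > 20"%, or stopping renal replacement therapy. The two creatinine limbs name neither a laboratory nor the source of the ULN.

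**Baseline in the SAP.** SAP 2.5 states: "The baseline of a laboratory parameter will be based on the central laboratory values except for platelet count". On timing it states: "In general, the baseline of a study endpoint is the last observation prior to the first study drug administration except for platelet count". Creatinine is not an exception to either rule, so its baseline is the last central value before first dose.

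**Baseline in the Protocol.** Protocol 13.2.1 states: "The baseline creatinine is defined as the maximum creatinine value between the diagnosis of TMA and 4 weeks after the first dose of OMS721". No laboratory is named.

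**Follow-up values.** A patient responds by meeting the criteria at any time after baseline. Protocol 13.2.5.1 and SAP 2.8.2.1 both say that "laboratory values collected from both the local laboratories and the central laboratories will be used to determine response status".

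**Supply of values.** Protocol 19.5 collects local results, as available: "Daily from 28 days prior to the diagnosis of TMA to the later of 12 weeks following the diagnosis of TMA" (or 4 weeks after TMA resolution, if later). For creatinine, Table 2 in Protocol 19.4 adds: "Overlapping data will also be available from the central laboratory on some dates". Protocol 19.3 schedules chemistry at 7 visits after Day 1 in Stage 2 alone (T-2 to T-4, F-1 to F-4), or 11 if the patient enters Stage 3 (T-2 to T-8, F-1 to F-4).

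**The concern.** A percentage fall measures change in the patient only if both readings are on the same scale. Under the SAP, baseline is central, while most follow-up values are likely to be local, because local results are gathered daily where available and central results only at visits. Any systematic difference between the two laboratories then enters the computed fall.

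The plan handles laboratory source elsewhere. The change-from-baseline creatinine endpoint is restricted to central values (Protocol 7.3.2, SAP 2.1), and SAP 2.5 has a central-first rule for baseline platelets. The responder definition has no equivalent for creatinine.

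At stake is whether a patient counts as a renal responder. That is one of several routes to the clinical part of the primary response, but the whole clinical part of the first alternative response (Protocol 13.2.5.1, SAP 2.8.2.1), which is meant as a sensitivity analysis and carries the same weakness.

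**Working it through.** **The plan's own figure.** Exact (Clopper-Pearson) 95% intervals for n = 28 have widths from 12.3% to 38.7%, and 14/28 gives 30.6% to 69.4%. Both match Protocol 13.1 and SAP 1.3. The documents give no figure for a between-laboratory difference, so the ratios below are assumptions.

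**SAP baseline: central baseline, local follow-up.** Let r be the local reading divided by the central reading, t the true fall and f the nominal threshold.

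- Observed fall = 1 − r(1 − t)
- Setting this equal to f gives the true fall that just passes: t = 1 − (1 − f)/r

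| r | f = 20% | f = 40% |
|---|---|---|
| 0.97 | 1 − 0.8/0.97 = 17.5% | 1 − 0.6/0.97 = 38.1% |
| 0.95 | 15.8% | 36.8% |
| 0.90 | 11.1% | 33.3% |
| 1.00 | 20.0% | 40.0% |
| 1.05 | 23.8% | 42.9% |

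A central follow-up value always needs 20% or 40%. With both readings from one laboratory, r cancels and the nominal thresholds hold.

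**Direction.** Take r = 1.05 and a true fall of 22% seen only on a day with a local result. The observed fall is 1 − 1.05 × 0.78 = 18.1%, which misses the 20% threshold. Local against local it is 22% and passes that threshold. The current rule can therefore lose a patient as well as gain one.

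**Where the 20% figures apply.** That limb also requires creatinine below ULN. From baseline B, reaching ULN needs a fall of 1 − ULN/B, which equals 20% at B = 1.25 × ULN. Above that, the ULN condition is the harder one. The boundary is approximate because the ULN source is not stated: if a local ULN is used and is lower in the same ratio r, the boundary becomes 1.25 × r × ULN, or 1.125 × ULN at r = 0.90. The 40% limb has no such restriction.

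**Protocol baseline: maximum, no laboratory named.** Suppose the local laboratory reads high by a factor h and supplies the maximum, and a central value shows the fall. Then t = 1 − (1 − f)h.

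- h = 1.05: 1 − 0.8 × 1.05 = 16.0%, and 1 − 0.6 × 1.05 = 37.0%
- h = 1.10: 12.0% and 34.0%

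Taking a maximum over both laboratories favours the higher-reading one at baseline. Settling the time point alone therefore does not settle the laboratory question.

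**Link to the decision rule.** Efficacy is declared if the exact lower bound exceeds 15%. The lower limit is 13.2% for 8/28 and 15.9% for 9/28, so one reclassified patient changes the conclusion only at that boundary.

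**The case against.** The strongest objection is that the central baseline is not the trial's settled rule. Protocol 13.2.1 gives a maximum over a window that starts at TMA diagnosis and names no laboratory, so the first table does not apply under it as it stands. This is right, and it means the two sections must be reconciled first. It does not remove the point, since the Protocol's rule also leaves laboratories unpaired.

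A reader might infer that mixing laboratories can only add responders. That is true against an analysis restricted to central values. It is not true against same-laboratory comparison, as the 22% example shows.

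A reader might also infer that no same-day rule exists after baseline. SAP 2.6 has one for platelet counts and hemoglobin: the first measure of the day, chosen because of transfusions. It does not cover creatinine and does not rank laboratories. Imposing a central-first rule on platelets would override that safeguard when the central draw is later, so there is no case for changing it here.

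Three further limits stand. Local collection is as available, and its 12 weeks run from diagnosis rather than first dose, so daily coverage after baseline may be shorter. A reclassified patient must be evaluable for renal function, meet the platelet and LDH criteria, and have no other qualifying clinical limb. The central-only creatinine endpoint and the per-patient listing of each criterion would let a reader see part of the problem.

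**Conclusion.** The point holds in limited form. Followed as written, the SAP allows a central creatinine baseline to be compared with a local value, and nothing in either document prevents a laboratory difference from counting as change in the patient. For a local laboratory reading 3% to 10% low, the true fall needed is 17.5% to 11.1% instead of 20% (baseline at or below about 1.25 × ULN), and 38.1% to 33.3% instead of 40%. For one reading 5% high, local values need 23.8% or 42.9%. These sizes rest on assumed ratios and on the qualifying value being local.

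A reader might conclude that the primary result is in doubt. The documents do not support that. The number of patients who depend on the renal limb alone is unknown, and one patient matters only between 8 and 9 responders of 28; at the plan's illustrative 50% rate the lower limit is 30.6%. The effect bears most directly on the first alternative response. The change is still worth making, because it closes a gap in a primary-endpoint rule at little cost.

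**What to change.** 1. Reconcile the creatinine baseline between Protocol 13.2.1 and SAP 2.5, stating both the time window and the laboratory.
2. In SAP 2.8.2.1, compute creatinine reduction only between results from the same laboratory: local against the patient's local baseline, central against the central baseline. Apply that laboratory's own ULN.
3. When both laboratories report creatinine on the same date, use the central result.
4. Leave the first-of-day rule for platelets in SAP 2.6 unchanged.

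The cost is SAP wording and one extra derived variable, the local creatinine baseline. No new data are needed: local creatinine around TMA diagnosis is already collected as available. The downside is that a patient with no local baseline value is judged on central values only, which means fewer occasions on which to show a fall.

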7.3.2. Secondary Endpoints

The secondary endpoints are to evaluate the following in patients with HSCT-TMA treated with OMS721:

- Duration of response, defined as the number of days from the first response date to the first relapse date

CONFIDENTIAL

No use, disclosure or reproduction outside of Omeros without prior written authorization

- 100-day survival, from the date of TMA diagnosis
- Overall survival, from the date of TMA diagnosis
- Freedom from platelet transfusion defined as no platelet transfusions for at least 4 weeks following the last platelet transfusion except for patients who died within 4 weeks of the last platelet transfusion (only evaluated in patients who had platelet transfusions in the 2 weeks prior to or on the first OMS721 dose date)
- Freedom from RBC transfusion defined as no RBC transfusions for at least 4 weeks following the last RBC transfusion except for patients who died within 4 weeks of the last RBC transfusion (only evaluated in patients who had RBC transfusions in the 2 weeks prior to or on the first OMS721 dose date)
- Change from baseline in platelet count (post baseline platelet counts without platelet transfusions 2 days before and on the day of the platelet count collection will be used) over time using central laboratory values
- Change from baseline in LDH over time using central laboratory values
- Change from baseline in haptoglobin over time using central laboratory values
- Change from baseline in Hgb (post baseline Hgb without RBC and whole blood transfusions 6 days before and on the day of the Hgb collection will be used) over time using central laboratory values
- Change from baseline in creatinine over time using central laboratory values
- The PK of multiple-dose administration of OMS721 (this will be assessed in patients with HSCT-TMA as well as patients with aHUS and TTP)
- The PD of multiple-dose administration of OMS721 (this will be assessed in patients with HSCT-TMA as well as patients with aHUS and TTP)
- The immunogenicity of multiple-dose administration of OMS721 (this will be assessed in patients with HSCT-TMA as well as patients with aHUS and TTP)

7.3.3. Exploratory Endpoints

The exploratory endpoints are:

- Assess the effect of baseline circulating MBL levels on PK and PD measures in patients with HSCT-TMA, aHUS, and TTP
- Assess the effect of baseline circulating MASP-2 levels on PK and PD measures in patients with HSCT-TMA, aHUS, and TTP
- Describe the effect of OMS721 on TMA laboratory markers in patients with aHUS and TTP

7.4. Study Extension

Patients completing the treatment period of Stage 2 may be eligible for continued OMS721 treatment in Stage 3. Patients may be eligible for extension of their treatment with OMS721 in

CONFIDENTIAL

No use, disclosure or reproduction outside of Omeros without prior written authorization

Stage 3 if they are deriving clinical benefit, have not displayed any signs or symptoms of serious toxicity, and the Investigator and Sponsor's medical monitor agree that the patient may derive benefit from continuing treatment in Stage 3. The primary objective of the Stage 3 extension is to provide a treatment option that may be better than alternative treatments. A secondary objective of this extension is to assess safety and efficacy parameters of OMS721 during extended treatment.

The decision to offer extended treatment will be made on a case-by-case basis and will be implemented under the following guidelines:

- The patient provides informed consent for further treatment.
- The benefit-to-risk assessment is positive for the patient.

The patient's treating Investigator and the Sponsor's medical monitor will determine eligibility for Stage 3 based upon the patient's response to therapy and safety and tolerability prior to the last scheduled treatment visit in Stage 2 in order to determine the appropriate PK draws following that visit.

8. SELECTION AND WITHDRAWAL OF PATIENTS

8.1. Patient Inclusion Criteria

Patients may be included in the study only if they meet all of the following criteria:

1. Competent to provide informed consent.
2. Voluntarily provide informed consent in accordance with regulations and governing ethics committee requirements prior to any procedures or evaluations performed specifically for the sole purpose of the study.
3. Are age \geq 18 years at screening (Visit 1).
4. Have a diagnosis of TMA in accordance with one of the following 3 categories:
 - As of Amendment 10 of this protocol, enrollment of aHUS patients was closed. Primary aHUS, diagnosed clinically and having ADAMTS13 activity $>$ 10% in plasma. Patients are eligible with or without a documented complement mutation or anti-complement factor H (anti-CFH) antibody. Patients are categorized according to their response to plasma therapy (plasma exchange or plasma infusion):
 - Plasma therapy-resistant aHUS patients must have all of the following:
 - Screening platelet count $<$ 150,000/ μ L despite at least 4 plasma therapy treatments prior to screening
 - Evidence of microangiopathic hemolysis (presence of schistocytes, serum LDH $>$ ULN, or haptoglobin $<$ lower limit of normal [LLN])
 - Serum creatinine $>$ ULN

CONFIDENTIAL

No use, disclosure or reproduction outside of Omeros without prior written authorization

- Chronic plasma therapy-responsive aHUS patients (plasma therapy-sensitive) must require at least once-per-week plasma therapy for 4 weeks before first dose of OMS721 with serum creatinine > ULN.
- As of Amendment 10 of this protocol, enrollment of TTP patients was closed. TTP defined as having all of the following:
 - Platelet count < 150,000/ μ L
 - Evidence of microangiopathic hemolysis (presence of schistocytes, serum LDH > ULN, or haptoglobin < LLN)
 - ADAMTS13 activity \leq 10% during the current episode of TTP or historically
- Persistent HSCT-associated TMA defined as having all of the following at least 2 weeks following modification or discontinuation of calcineurin inhibitor treatment or at least 30 days after the transplant:
 - Platelet count < 150,000/ μ L
 - Evidence of microangiopathic hemolysis (presence of schistocytes, serum LDH > ULN, or haptoglobin < LLN)
 - Renal dysfunction (doubling of serum creatinine from pre-transplant)
- 5. No clinically apparent alternative explanation for thrombocytopenia and anemia.
- 6. If sexually active and of childbearing potential, must agree to practice a highly effective method of birth control until the end of the study, defined as one that results in a low failure rate (i.e., less than 1% per year) when used consistently and correctly, such as implants, injectables, combined oral contraceptives, some intrauterine devices, sexual abstinence, or vasectomized partner.

